The primary outcome of this repeated measures RCT is the proportion of participants accurately identifying alcohol as a clear risk factor for breast cancer at 4-weeks post-randomisation. Inferences about the effect of the Health4Her intervention on the primary outcome will be based on a comparison, between treatment groups, of change from baseline to 4-weeks post-randomisation using a Cochran-Mantel-Haenszel test. This analysis tests for homogeneity of the odds ratio across strata (i.e. intervention and control). A binomial test (that is, a test of proportions) will be used as an ancillary analysis of the primary outcome (i.e. the difference in proportions between the two groups at 4-weeks post-randomisation).

Relevant covariates (from the list of potential covariates below) may also be used in further analysis, using generalised linear models (logistic regression) to make comparisons. Additional analyses may use covariates for post-stratification.

Secondary Outcomes

Alcohol Consumption

Alcohol consumption will be assessed by the Alcohol 14-day Timeline Follow-back (TLFB). Heavy drinking days are measured as >40 grams of alcohol (>4 Australian standard drinks). Alcohol consumption will also assessed by the AIHW alcohol frequency quantity items. Assessments are made at 0, 4 and 12 weeks and linear mixed models (continuous variables) or GLMMs or GAMMs (categorical / binary variables) will be used. The following outcomes will be analysed (transformed if necessary for analysis):

Secondary outcome 1 – Proportion of participants drinking less than or equal to 10 standard drinks per week at 4-weeks and 12-weeks post-randomisation. Derived from (operationalised in two ways):

- Has the participant consumed >10 standard drinks in week one AND/OR >10 standard drinks in week two? (tlfb_nhmrc_both_comprh)
- Has the participant consumed >10 standard drinks in both week one AND week two? (derived variable: tlfb_nhmrc_bothwks)

Secondary outcome 2 – Proportion of participants drinking less than or equal to 10 standard drinks per week at 4-weeks and 12-weeks post-randomisation, among only participants who drink more than 10 standard drinks per week at baseline.

Subgroup defined as either i. women who consumed >10 standard drinks in week one AND/OR >10 standard drinks in week two (tlfb_nhmrc_both_comprh) or ii. women who consumed >10 standard drinks in both week one AND week two (tlfb_nhmrc_bothwks).

Outcome derived from:

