- Has the participant consumed >10 standard drinks in week one AND/OR >10 standard drinks in week two? (tlfb_nhmrc_both_comprh)
- Has the participant consumed >10 standard drinks in both week one AND week two? (tlfb_nhmrc_bothwks)

Secondary outcome 3 – Change in alcohol consumption at 4-weeks and 12-weeks post-randomisation. Derived from:

- TLFB: Drinking Days (tlfb_drinkdays)
- TLFB: Drinking Days with > 2 Standard Drinks (tlfb_days_2stand)
- TLFB: Drinking Days with > 4 Standard Drinks (tlfb_days_4stand)
- TLFB: Total Standard Drinks in the Past 14 days (tlfb_totalmonth)
- Derived from AIHW frequency quantity items: average standard drinks per day (derived variable: alc_perday)
- AIHW frequency: In the past month, how often did you have an alcoholic drink of any kind? (alc_freq)
- AIHW quantity: quantity of alcohol consumed on a typical day calculated in standard drinks (alc_quant_sd)

Secondary outcome 4 – Change in alcohol consumption at 4-weeks and 12-weeks postrandomisation, among only participants who drink more than 10 standard drinks per week at baseline

Subgroup defined as either i. women who consumed >10 standard drinks in week one AND/OR >10 standard drinks in week two (tlfb_nhmrc_both_comprh) or ii. women who consumed >10 standard drinks in both week one AND week two (tlfb_nhmrc_bothwks).

Outcome derived from:

- TLFB: Drinking Days (tlfb_drinkdays)
- TLFB: Drinking Days with > 2 Standard Drinks (tlfb_days_2stand)
- TLFB: Drinking Days with > 4 Standard Drinks (tlfb_days_4stand)
- TLFB: Total Standard Drinks in the Past 14 days (tlfb_totalmonth)
- Derived from AIHW frequency quantity items: average standard drinks per day (alc_perday)
- AIHW frequency: In the past month, how often did you have an alcoholic drink of any kind? (alc_freq)
- AIHW quantity: quantity of alcohol consumed on a typical day calculated in standard drinks (alc_quant_sd)

Alcohol health literacy

Secondary outcome 5 – Change in participants' attitudes regarding alcohol and breast cancer risk from baseline to 4-weeks post-randomisation. A linear mixed model (for repeated measures) will be used to analyse the Likert scale response (derived from atttd_alcrisk). Transformations of response variables will be used as appropriate, such as in GLMMs or GAMMs.

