 - derived from atttd_changerisk
 - Likert response

Potential covariates for exploratory analyses of primary and secondary outcomes

- age (continuous; categorical 40-49, 50-59, 60-69, 70+ years)
- lgbtq+
- education
- born in Australia
- culturally and linguistically diverse background
- household composition
- disability status
- alcohol consumption at baseline (drinking above/within current NHMRC guidelines, 14-day TLFB subscales scores, AIHW frequency quantity scores)
- QoL/health-related QoL at baseline (SF-12 mental and physical component scores, EUROHIS-QOL single item)
- health literacy at baseline (attitude and knowledge scores)

ⁱGraeme Tucker, Robert Adams, David Wilson. New Australian population scoring coefficients for the old version of the SF-36 and SF-12 health status questionnaires, Qual Life Res (2010) 19:1069-1076, DO 10.1007/s11136-010-9658-9

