**At 4-weeks and 12-weeks post-randomisation:**

- *Proportion of participants drinking less than or equal to 10 standard drinks per week (i.e. within current Australian Alcohol Guidelines) (14-day Timeline Followback; TLFB)*
- *Among participants who drink more than 10 standard drinks per week at baseline: Proportion of participants drinking less than or equal to 10 standard drinks per week (14-day TLFB)*
- *Change in alcohol consumption (14-day TLFB; AIHW alcohol frequency/quantity items)*
- *Among participants who drink more than 10 standard drinks per week at baseline: Change in alcohol consumption (14-day TLFB; AIHW alcohol frequency/quantity items)*
- *Change in general health (SF-12)*
- *Change in quality of life (EUROHIS-QOL single item)*

We hypothesise that compared to those in the control group, at 4-weeks and 12-weeks post-randomisation:

- (iv) A significantly greater proportion of participants receiving alcohol brief intervention will be drinking less than or equal to 10 standard drinks per week (i.e. within current Australian Alcohol Guidelines)

- 
- (v) Of participants who drink more than 10 standard drinks per week, a significantly greater proportion of those receiving alcohol brief intervention will be drinking less than 10 standard drinks per week
  - (vi) Participants receiving alcohol brief intervention will report significantly greater reductions in alcohol consumption
  - (vii) Of participants who drink more than 10 standard drinks per week, those receiving the alcohol brief intervention will report significantly greater reductions in alcohol consumption
  - (viii) Participants receiving alcohol brief intervention will report significantly greater improvements in general health and quality of life

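### Secondary outcome 2 uses one cut-off for entry and for success, so its binary baseline carries no information; baseline TLFB total should be a committed covariate in a model of weeks 4 and 12

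*SAP*

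**What the plan says.** In the SAP, under Secondary Outcomes, Alcohol Consumption, secondary outcome 2 is the proportion at or below 10 standard drinks per week at 4 and at 12 weeks, "among only participants who drink more than 10 standard drinks per week at baseline". The subgroup has two forms: "Subgroup defined as either i. women who consumed >10 standard drinks in week one AND/OR >10 standard drinks in week two", "or ii. women who consumed >10 standard drinks in both week one AND week two (tlfb_nhmrc_bothwks"). The follow-up coding rests on the same two variables: "Has the participant consumed >10 standard drinks in week one AND/OR >10 standard drinks in week two? (tlfb_nhmrc_both_comprh") or "Has the participant consumed >10 standard drinks in both week one AND week two? (tlfb_nhmrc_bothwks"). The SAP does not say which subgroup form goes with which coding, so four pairings are open. Each assessment covers one 14-day window (Protocol 9.2.2.1), at 0, 4 and 12 weeks.

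The same SAP section assigns binary alcohol outcomes to a GLMM or GAMM. The SAP's general text on outcomes with more than two time points specifies treatment, time and their interaction, and an overall group-by-time test over weeks 0, 4 and 12. Baseline TLFB amounts appear only in the list headed "Potential covariates for exploratory analyses of primary and secondary outcomes".

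Hypothesis (v) in Protocol 3.2 is a comparison with control: "a significantly greater proportion of those receiving alcohol brief intervention will be drinking less than 10 standard drinks per week". (It says less than 10, whereas the outcome also allows exactly 10.)

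**The concern.** A woman enters because one baseline fortnight lay above 10 and succeeds because a later fortnight does not. Women who start just above 10 will often cross with no change in habit; women far above seldom will. Distance above 10 at baseline is therefore a strong predictor of the outcome, and the committed model does not use it.

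The binary baseline cannot stand in for that distance. When subgroup and outcome share a definition, everyone in the subgroup is a failure at week 0 in both arms. A logistic model that treats week 0 as a time point then has nothing to estimate there, and the interaction contrasts against week 0 are not identified. When the definitions differ (either-week subgroup, both-weeks coding), women with exactly one heavy week already count as successes at baseline.

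At stake is the precision of the test of hypothesis (v), in a subgroup for which the trial was not sized.

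**Working it through.** **1. The plan's own figure.** Protocol 14.1 sizes only the knowledge endpoint. With 0.22 v 0.34, two-sided 0.05 and 80% power:

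n = [1.96√(2×0.28×0.72) + 0.8416√(0.22×0.78 + 0.34×0.66)]² / 0.12² = 219 per arm; 219/0.80 = 274 per arm, 548 in total.

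This reproduces exactly. The documents give no corresponding figure for secondary outcome 2.

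**2. Assumptions.** The documents give no TLFB variance, correlation or prevalence of drinking above 10. Assumed here: 80% of women drink; weekly drinks among drinkers are lognormal with median 5 and between-woman log-SD 0.9; four settings of week/visit log-SD are used. There is no intervention effect and no change in habit.

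**3. Share at or below the cut-off at week 4 with no effect (simulation, matched definitions).**

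| Week/visit log-SD | Either-week | Both-weeks |
|---|---|---|
| 0.2/0.1 | 15% | 17% |
| 0.3/0.2 | 22% | 27% |
| 0.4/0.3 | 28% | 36% |
| 0.5/0.4 | 33% | 44% |

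**4. Sensitivity.** With the same four settings but medians of 3-8 and between-woman log-SD of 0.8-1.2, matched rates run from 8% to 61%. Under the step 2 inputs, the either-week subgroup with both-weeks coding gives 32-59%, and 28-48% of that subgroup already count as successes at baseline. The reverse pairing gives 5-20%. A separate latent-normal model (10-30% of weeks above 10, correlation between weeks 0.60-0.95) gives 3-82% over all four pairings.

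**5. Bias.** In 4,000 null two-arm trials of 279 per arm (latent-normal model, 20% of weeks above 10, correlation 0.8), the mean rates in the two arms agreed to within about one point for every pairing, and type I error was 4.2-4.6%.

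**6. Dilution.** Suppose the intervention moves 20% of the women who would otherwise still exceed 10. The arm difference is 0.20×(1 − p), where p is the no-effect rate: 17, 14 or 11 points at p = 15, 30 or 45%. With an assumed 60 women per arm and p = 0.15 v 0.32:

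- SE under the null = √(2×0.235×0.765/60) = 0.0774
- SE under the alternative = √((0.1275 + 0.2176)/60) = 0.0758
- power = Φ[(0.17 − 1.96×0.0774)/0.0758] = Φ(0.24) = 60%

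The same sum gives 35% and 22% for the other two rates.

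**7. What baseline amount adds.** At 0.3/0.2, women with a baseline 14-day total of 24 or less are 37% of the either-week subgroup, and 44% of them cross at week 4 with no effect. Above 40 drinks, 1% do.

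**8. Power of a two-visit model (weeks 4 and 12).** Women followed: 558×0.80 = 446, giving an either-week subgroup of about 104 (0.3/0.2) or 114 (0.4/0.3). A GEE stands in for the GLMM; the covariate is log baseline 14-day total.

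| True cut in drinking | Log-SDs | Unadjusted | Adjusted | Gain (points) |
|---|---|---|---|---|
| 20% | 0.3/0.2 | 40% | 59% | 19 |
| 20% | 0.4/0.3 | 35% | 45% | 10 |
| 30% | 0.3/0.2 | 77% | 95% | 18 |
| 30% | 0.4/0.3 | 69% | 83% | 14 |

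Type I error was near 5%. A separate run of the 20% scenarios gave 44% to 61% and 32% to 43%, so single entries carry a few points of simulation error.

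**The case against.** The strongest reply is that the SAP already has a better analysis of these women. Secondary outcome 4 takes change in amount in the same subgroup, by linear mixed models that keep baseline as a time point. Under the same assumptions, a comparison of change in log 14-day total at week 4 has 81% (0.3/0.2) or 53% (0.4/0.3) power for a 20% cut, and about 100% or 90% for a 30% cut. That stands: secondary outcome 2 is not the only view of the subgroup, and a null result on it would not be read alone. It does not repair secondary outcome 2, which has its own hypothesis.

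Second, 10 drinks is the guideline limit, so the outcome measures adherence to a guideline and owes no minimum reduction. That also stands, and the cut-off is not criticised here.

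Third, the trial is powered only for knowledge, and Protocol 14.1 treats drinking within guidelines as an exploratory proximal marker. This limits the weight of the point, but the remedy costs almost nothing.

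Fourth, comparing adjusted and unadjusted models at week 4 alone would misstate the plan, which commits to repeated measures. Step 8 therefore uses two visits.

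**Conclusion.** The point holds as one of efficiency and model specification. The committed analysis leaves out a strong predictor that is already collected, and with matched definitions a group-by-time test including week 0 has no baseline variation to use. Under the assumed model, adjustment is worth roughly 10-19 points of power.

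A reader might infer more, and the documents do not support it:

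- That the comparison of arms is biased. It is not: selection precedes randomisation and acts equally in both arms.
- That 15-45% is a property of this trial. It follows from the inputs in step 2, for matched definitions only. Step 4 shows how far it moves, and Protocol 14.1 leaves the prevalence of risky drinking for the trial to estimate.
- That a within-arm response claim is planned. Hypothesis (v) is stated against control.
- That success must be confirmed at both follow-up calls. Under the same assumptions, a confirmed response has about the same power as a single visit (69% v 69%, and 57% v 55%, for a 30% cut).

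The subgroup size is also assumed: 94-125 women over the four settings, and 33-62 if the median is 3.

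**What to change.** In SAP secondary outcome 2:

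1. Keep the repeated-measures binary model (GLMM), but fit it to weeks 4 and 12 only. Compare the arms overall and at each visit, in place of a group-by-time test that includes week 0.
2. Make the log of baseline tlfb_totalmonth a committed covariate. Every woman in the subgroup exceeded 10 drinks in at least one baseline week, so the log is always defined.
3. Use the same week definition for subgroup and outcome: either-week with either-week, or both-weeks with both-weeks.
4. Show adjusted proportions or a risk difference beside the odds ratio, which is conditional on baseline drinking.

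The cost is SAP wording and one covariate; no new data are needed. A confirmed-response endpoint, or a statement restricting within-arm reporting, is optional and not needed to resolve this point.

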---

### Revision Chronology:

Date of change	Summary of changes
1 st February 2019	Version 1: original document
16 th July 2019	Version 2: update to section 5.3 Recruitment and identification of potential participants , addition of researcher script, conduct formative evaluation focus groups/surveys with Lifepool, clarification of subsample to complete alcohol consumption/intervention feasibility questions, increase number of participants to power the pilot trial (update power and sample size calculation), refine aims, update alcohol items, add protocol for providing contact details for additional support as required, add implied consent via use of a iPad landing page, add VicHealth funder, update title, update timeline.
29 th July 2019	Version 3: references to PICF in sections 8.1 and 8.2 changed to refer to Participant Information Sheet (PIS; consent provided via iPad landing page)
27 th August 2019	Version 4: Addition of donation to breast cancer research for pre-trial feasibility survey / focus group participation
19 th January 2021	Version 5: refined study outcomes and measures. Updated power and sample size calculation, and data analysis plan. Minor changes to inclusion/exclusion criteria. Refined title and description of the intervention. Added verbal consent procedure to replace iPad landing consent page. Added Eastern Health COVID-19 safety procedures at Maroondah BreastScreen. Updated project timeline.
12 th May 2020	Version 6: introduced potential for participants to provide written consent when recruitment is busy. Added process whereby Maroondah BreastScreen reception provide a reminder text message or phone call prior to recruitment days and flag the study occurring onsite.
8 th August 2020	Version 7: Minor changes to protocol based on trial procedures in practice; updated description of data collection to more accurately reflect functionality of REDCap and use/security of identifiable and re-identifiable data.

### Sponsor

Eastern Health

### Funded By

2019 Easter Health Foundation Research and Innovation Grant  
2019 VicHealth Impact Research Grant

### Statement of Compliance

This document is a protocol for a research project. This study will be conducted in compliance with all stipulation of this protocol, the conditions of the ethics committee approval, the NHMRC National Statement on Ethical Conduct in Human Research (2007) and the Note for Guidance on Good Clinical Practice (CPMP/ICH-135/95).

---

TITLE	Health4Her: Increasing knowledge of alcohol as a risk factor for breast cancer among women attending breast screening services
OBJECTIVES	Alcohol consumption is a major modifiable risk factor for breast cancer in women. Research demonstrates a strong link between alcohol and breast cancer risk, even at low drinking levels. This project aims to reduce alcohol consumption among women attending an Eastern Health BreastScreen service for routine mammography.
DESIGN	Pragmatic randomised controlled trial
OUTCOMES	
Baseline, 4-week and 12-week measures will be administered.
 
PRIMARY OUTCOME At 4-weeks post-randomisation, proportion of participants in the active condition (relative to control) accurately identifying alcohol as a clear risk factor for breast cancer.
 
SECONDARY OUTCOMES At 4-weeks post-randomisation:
 
 
- Change in participants' attitudes regarding alcohol and breast cancer risk (items adapted from previous literature, e.g. Fisher et al. 2017)
 
- Proportion of participants accurately identifying i) the amount of alcohol in an Australian standard drink; ii) the number of standard drinks in an average restaurant serve of red wine; iii) the maximum number of standard drinks per week recommended by current Australian Alcohol Guidelines (items adapted from previous literature, e.g. Bowden et al. 2014)
 
- Proportion of participants who have accessed health information on i) alcohol harms, ii) alcohol and breast cancer risk, and iii) alcohol harm-reduction
 
 
At 4-weeks and 12-weeks post-randomisation:
 
 
- Proportion of participants drinking less than or equal to 10 standard drinks per week (i.e. within current Australian Alcohol Guidelines) (14-day Timeline Followback; TLFB)
 
- Among participants who drink more than 10 standard drinks per week at baseline: Proportion of participants drinking less than or equal to 10 standard drinks per week (14-day TLFB)
 
- Change in alcohol consumption (14-day TLFB; AIHW alcohol frequency/quantity items)
 
- Among participants who drink more than 10 standard drinks per week at baseline: Change in alcohol consumption (14-day TLFB; AIHW alcohol frequency/quantity items)
 
- Change in general health (SF-12) and quality of life (EUROHIS-QOL single item)
 

	
Feasibility of implementing alcohol brief intervention in a breast screening setting will be assessed through formative, process and impact evaluation, examining factors such as:
 
 
- The proportion of patients who agree to receive alcohol health promotion
 
- Acceptability of the intervention prototype and research procedures
 
- Women’s attitudes toward receiving alcohol health promotion intervention in the BreastScreen setting
 
- Staff feedback on alcohol health promotion intervention implemented in the breast screen setting
 

STUDY DURATION	2.5 years
INTERVENTIONS	
Active: The intervention arm will receive 4 minutes of alcohol brief intervention, and 3 minutes of lifestyle health promotion (physical activity; maintaining a healthy weight), to increase knowledge of how to improve women's health and reduce breast cancer risk. Alcohol and lifestyle information will be delivered by way of an animation on an iPad. Participant responses to questions about current alcohol use will branch to personalised feedback consistent with level of alcohol consumption (i.e. drinking within or above current Australian Alcohol Guidelines).
 
Take-home pamphlets - a pamphlet summarising the alcohol information presented during the animation, and a pamphlet on nutrition to maintain a healthy weight, will be provided.
 
Control: The control arm will receive 3 minutes of lifestyle health promotion (physical activity; maintaining a healthy weight) to increase knowledge of how to improve women's health and reduce breast cancer risk, not inclusive of alcohol information. Lifestyle information will be delivered by way of an animation on an iPad.
 
Take-home pamphlet - a pamphlet on nutrition to maintain a healthy weight will be provided.

# PARTICIPANTS	548 participants
POPULATION	
Inclusion criteria:
 
 
• Female, attending the BreastScreen setting for routine mammography
 
• 40+ years of age
 
• English as a first language or fluent
 
• Regular access to a telephone
 
• Able to provide informed consent to participate
 
• Any level of alcohol consumption (including non-drinkers)
 
 
Exclusion criteria:
 
 
• Hearing impairment sufficient to prohibit a telephone interview
 
• Pregnancy
 
• Not able to read or comprehend English to provide informed consent or receive the brief intervention
 

---

## 1 ADMINISTRATIVE INFORMATION

### 1.1. Trial registration

Trial to be registered with Clinicaltrials.gov, registration number: NCT04715516

### 1.2. Expected duration of study

This study is expected to take 24 months to complete.

#### Project Timeline – Health4Her

##### Jun 2019 – Feb 2021

**Study set-up:** (< Jun 2019: full protocol developed, ethics application submitted) finalise ethics approval, iOS software development, pamphlet development, full statistical analyses plan, randomisation schedule, REDCap database, RA recruitment and training, Maroondah BreastScreen site briefing

**(Sep 2019)** Set-up program evaluation, including formative evaluation with Lifepool

